4.4 EXPLORATORY ANALYSIS

The secondary efficacy endpoints will be evaluated as exploratory analyses for the MRI-active subgroup.

The primary and secondary endpoints will also be evaluated in the following patient subgroups of all randomized patients unless otherwise stated, as exploratory analyses:

- Age ≤ 55 versus > 55 years
- EDSS score ≤ 6.5 versus > 6.5
- MRI-inactive versus MRI-active

- Males and females (all randomized patients, MRI-active subgroup and MRI-inactive subgroup)
- Region European Union, United Kingdom, and Canada versus other

All results will be summarized in a forest plot.

The estimands will have the same attributes (except for the Population attribute) and estimation method as for the corresponding primary or secondary endpoints (Section 4.2.2 Section 4.3.1).

The following endpoints will be evaluated in all randomized patients and the MRI-active subgroup as exploratory analyses:

- Change from baseline to Week 120 in fatigue as measured by Modified Fatigue Impact Scale (MFIS)
- Annual rate of percent change from baseline and from Week 24 in cervical spinal cord volume on MRI scans
- Change from baseline to Week 120 in a measure of manual ability for adults with upper limb impairments (ABILHAND)
- Change from baseline to Week 120 in the upper limb domain of a life quality measure for patients with neurological disorders (Quality of Life in Neurological Disorders-Upper Extremity Function [Neuro-QoL-UE])
- Patient Global Impression of Change for upper limb function (PGIC-UL) at each scheduled visit until Week 120
- Patient Global Impression of Change for fatigue (PGIC-F) at each scheduled visit until Week 120
- Change from baseline to Week 120 in the Multiple Sclerosis Impact Scale (MSIS)29 physical domain score
- Occurrence of a ≥ 7.5 -point increase (worsening) in MSIS-29 physical domain transformed total scores at each scheduled visit until Week 120
- Time to a ≥ 4 -point decrease (worsening) in SDMT sustained for 24 weeks
- Time to a ≥ 8 -point decrease (worsening) in SDMT sustained for 24 weeks
- Time to 24-week CDP
- Time to 24-week CDP or a ≥ 4 -point decrease (worsening) in SDMT sustained for 24 weeks
- Time to 24-week CDP or a ≥ 8 -point decrease (worsening) in SDMT sustained for 24 weeks
- Change from baseline to Week 120 in the SDMT

The PGIC-UL is a single item questionnaire completed by the patient to assess upper limb function compared with the function over the last 6 months. The patient will be asked to rate their upper limb function using a 7-point Likert scale ranging from “very much better” (1) to “very much worse” (7).

PGIC-F

The PGIC-F is a single item completed by the patient to assess changes in fatigue over the last 6 months. Patients will be asked to respond on a 7-point Likert scale from “very much better” (1) to “very much worse” (7).

MSIS-29

The MSIS-29, v2 is a 29-item patient-reported measure of the physical and psychological impacts of MS. Patients are asked to rate how much their functioning and well-being has been impacted over the past 14 days on a 4-point scale, from “Not at all” (1) to “Extremely” (4).

MSIS-29 physical impact and MSIS-29 psychological impact scores will be derived as per the MSIS-29v2 scoring manual ([appendix - MSISv1 and v2 scoring instructions](#)).

The MSIS-physical impact observed score is the sum of items 1-20. The MSIS-physical impact score will be transformed onto a 0 to 100 scale using the following formula:

$$\frac{100 \times (\text{'Physical scale – raw' – min possible score})}{\text{max possible score – min possible score}} = \frac{100 \times (\text{observed score} – 20)}{80 – 20}$$

The MSIS-psychological impact observed score is the sum of items 21-29. The MSIS-psychological impact score will be transformed onto a 0 to 100 scale using the following formula:

$$\frac{100 \times (\text{'Psychological scale – raw' – min possible score})}{\text{max possible score – min possible score}} = \frac{100 \times (\text{observed score} – 9)}{36 – 9}$$

A higher score indicates a greater impact of MS.

For respondents with missing data, but where at least 50% of the items in a scale have been completed, a respondent-specific mean score computed from the completed items can be computed as described below.

For example, if a respondent has completed 15 items in the physical scale, the respondent-specific mean score is obtained as the sum of the completed items divided by 15. This value is then used as the score for each of the missing 5 items. The total score is then obtained as usual by summing the values of the 15 completed items and the 5 imputed items. Note: respondents must have completed a minimum of 10 items in the physical scale, or 5 items in the psychological scale to use this imputing process.

SDMT

The SDMT is a brief and easy to administer performance test that involves a simple substitution task. Using a reference key, the examinee has 90 seconds to pair specific numbers with given geometric figures. Responses will be collected orally. The SDMT total score is calculated as the number of correct responses. A higher score indicates greater cognitive functioning.

4.4.1 Estimands for Continuous eCOA Endpoints

Estimand: The estimand is the mean difference in the endpoint between the experimental and control arms in patients with PPMS, including patients later in their disease course, and regardless of adherence to the randomized treatment or use of another MS DMT or commercial ocrelizumab.

Endpoints:

- Change from baseline to Week 120 in fatigue as measured by MFIS
- Change from baseline to Week 120 in a measure of manual ability for adults with upper limb impairments (ABILHAND)
- Change from baseline to Week 120 in the upper limb domain of a life quality measure for patients with neurological disorders (Neuro-QoL-UE)
- Change from baseline to Week 120 in the MSIS-29 physical domain score
- Change from baseline to Week 120 in the SDMT

Summary Measure and Primary Estimator: MMRM will be used to quantify mean difference in the endpoints between the experimental and control arms. The fixed effects in the model will include independent variables of randomized treatment, visit, baseline outcome, treatment-by-visit interaction, baseline outcome by visit interaction, along with the randomization stratification factors. An unstructured variance-covariance structure will be applied to model the within-subject errors across visits. The restricted maximum likelihood (REML) method will be used for estimation of variance components. In the case of non-convergence, compound symmetry will be used, together with a robust estimator of standard error (“sandwich” estimator).

The statistical significance of the estimated mean difference will be calculated by using the Wald test.

In order to estimate the estimand of interest, the following intercurrent event handling strategies will be applied:

Withdrawal from treatment and no initiation of another MS DMT or commercial ocrelizumab: All data available will be included in the analysis following the treatment-policy strategy.

Withdrawal from treatment and initiation of another MS DMT or commercial ocrelizumab: All data available will be included in the analysis following the treatment-policy strategy.

The estimand for continuous electronic Clinical Outcome Assessments (eCOA) endpoints in the MRI-active subgroup will be similar except the population will be patients with PPMS, including patients later in their disease course, as defined by the study inclusion and exclusion criteria (see Sections 4.1.1 and 4.1.2 of the protocol), with MRI activity (see Section 2.1.1 of the protocol).

4.4.2 Estimands for Categorical eCOA Endpoints

Estimand: The estimand is the proportion of patients in each category at each scheduled visit until Week 120, in the experimental and control arms in patients with PPMS, including patients later in their disease course, and regardless of adherence to the randomized treatment or use of another MS DMT or commercial ocrelizumab.

Endpoints:

- PGIC-UL at each scheduled visit until Week 120
- PGIC-F at each scheduled visit until Week 120

Summary Measure and Primary Estimator: The number and proportion of patients in each category will be summarized at each scheduled visit until Week 120.

The same intercurrent event handling strategies as for the estimands for continuous eCOA endpoints (Section 4.4.1) will be applied.

The estimand for categorical eCOA endpoints in the MRI-active subgroup will be similar except the population will be patients with PPMS, including patients later in their disease course, as defined by the study inclusion and exclusion criteria (see Sections 4.1.1 and 4.1.2 of the protocol), with MRI activity (see Section 2.1.1 of the protocol).

4.4.3 Estimand for Proportion of Responders

Estimand: The estimand is the proportion of patients with a ≥ 7.5 -point increase (worsening) in MSIS-29 physical domain transformed total scores at each scheduled visit until Week 120 in the experimental and control arms in patients with PPMS, including patients later in their disease course, and regardless of adherence to the randomized treatment or use of another MS DMT or commercial ocrelizumab.

Endpoint:

- Occurrence of a ≥ 7.5 -point increase (worsening) in MSIS-29 physical domain transformed total scores at each scheduled visit until Week 120

Summary Measure and Primary Estimator: The number and proportion of patients with a ≥ 7.5 -point increase (worsening) in MSIS-29 physical domain transformed total scores will be summarized at each scheduled visit until Week 120.

The same intercurrent event handling strategies as for the estimands for continuous eCOA endpoints (Section 4.4.1) will be applied.

The estimand for proportion of responders in the MRI-active subgroup will be similar except the population will be patients with PPMS, including patients later in their disease course, as defined by the study inclusion and exclusion criteria (see Sections 4.1.1 and 4.1.2 of the protocol), with MRI activity (see Section 2.1.1 of the protocol).

4.4.4 Estimands for Time to Event Endpoints

Estimand: The estimand is the difference in time to the event, as expressed by the HR, between the experimental and control arms in patients with PPMS, including patients later in their disease course, regardless of adherence to the randomized treatment had the patients not initiated another MS DMT medication or commercial ocrelizumab

Endpoints:

- Time to a ≥ 4 -point decrease (worsening) in SDMT sustained for 24 weeks
- Time to a ≥ 8 -point decrease (worsening) in SDMT sustained for 24 weeks
- Time to 24-week CDP
- Time to 24-week CDP or a ≥ 4 -point decrease (worsening) in SDMT sustained for 24 weeks
- Time to 24-week CDP or a ≥ 8 -point decrease (worsening) in SDMT sustained for 24 weeks

All other estimand attributes and the estimation method will be identical as for the co-primary estimand 2 in Section 4.2.5 .

Missing assessments at scheduled visits prior to the last assessment of a patient, i.e. intermediate missing data, will not be imputed. For patients with an initial worsening, data collected at the next scheduled visit or treatment discontinuation visit will be used to confirm the worsening.

Missing data and patients without any events (including imputed events) during the double-blind treatment period will be handled similarly as for the co-primary estimand 1 in Section 4.2.2

The estimand for time to event endpoints in the MRI-active subgroup will be similar except the population will be patients with PPMS, including patients later in their disease course, as defined by the study inclusion and exclusion criteria (see Sections 4.1.1 and 4.1.2 of the protocol), with MRI activity (see Section 2.1.1 of the protocol).

4.4.5 Estimands for Rate of Change of Continuous MRI Endpoints

Estimand: The estimand is the mean difference in the endpoint between the experimental and control arms in patients with PPMS, including patients later in their disease course, where no treatment discontinuation nor initiation of another MS DMT or commercial ocrelizumab can occur.

Endpoints:

- Annual rate of percent change from baseline and from Week 24 in cervical spinal cord volume on MRI scans
- Annual rate of change from baseline in radius of total non-enhancing T1 lesion volume on MRI scan of the brain

The same population definition, intercurrent events handling strategies and estimator will apply as for the annual rate of change from baseline in radius of total volume of T2 lesions (Section 4.3.2).

The estimand for rate of change of continuous MRI endpoints in the MRI-active subgroup will be similar except the population will be patients with PPMS, including patients later in their disease course, as defined by the study inclusion and exclusion criteria (see Sections 4.1.1 and 4.1.2 of the protocol), with MRI activity (see Section 2.1.1 of the protocol).

4.4.6 Estimands for Expected Counts at each Scheduled Visit

Estimand: The estimand is the ratio of the mean endpoint between the experimental and control arms in patients with PPMS, including patients later in their disease course, where no treatment discontinuation nor initiation of another MS DMT or commercial ocrelizumab can occur.

Endpoints:

- The number of Gd-enhancing T1 lesions as detected by mandatory MRI, overall and at each scheduled visit
- The number of new or enlarging T2 hyperintense lesions as detected by mandatory MRI, overall and at each scheduled visit

Summary Measure and Primary Estimator: Separate negative binomial models will be fitted to the data on the endpoints at each scheduled visit and overall for the total count. The mean function of the model will be parameterized using the log link function and the linear predictor will include as an offset either the log number of MRI scans for Gd-enhancing T1 lesions or log time in years of scan relative to baseline for new or enlarging T2 hyperintense lesions, an indicator variable for the assigned treatment and the randomization stratification factors as independent variables. The statistical significance of the estimated ratio of means will be calculated by using the Wald test.

In order to estimate the aforementioned estimand, the same intercurrent event handling strategies as those for brain volume in Section 4.3.2 Section 4.3.3 will be applied.

The estimand for expected counts at each scheduled visit in the MRI-active subgroup will be similar except the population will be patients with PPMS, including patients later in their disease course, as defined by the study inclusion and exclusion criteria (See Sections 4.1.1 and 4.1.2 of the protocol), with MRI activity (see Section 2.1.1 of the protocol).

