4.5.10 Mandatory and Optional MRI Sequences

MRI will be used to monitor CNS lesions in patients with MS and potentially other pathophysiology, such as inflammation and neurodegeneration. Mandatory MRI scans (formally known as 'brain MRI') will be obtained in all patients at study visits as indicated in [Appendix 1](#), [Appendix 2](#), [Appendix 3](#), and [Appendix 4](#).

During the screening phase, two mandatory MRI scans (performed at least 6 weeks apart, but not more than 24 weeks apart) or one MRI with the mandatory sequences that can be compared with a historical MRI acquired in the previous 1 year will be performed to assess the patient's MRI activity level. MRI activity is defined as the presence of any T1 Gd+ lesion(s) and/or new and/or enlarging T2 lesion(s) during the screening period (see also Section 3.1). If the presence of new or enlarging lesions is ascertained, the patient will be stratified to the MRI-active subgroup. The MRI performed closer to randomization (i.e., either the second MRI scan at screening or the [only] screening MRI scan in the case where a historical scan was used for the assessment of MRI activity) will be considered as baseline MRI for the study analyses and will be captured under the baseline visit in the eCRF. Note that this baseline scan should be obtained maximum 6 weeks before but at least 10 days prior to performing the baseline visit to allow time for the centralized reading center to assess its quality and for potential re-scans if needed.

Postbaseline, the mandatory MRI scans will be obtained in all patients at Weeks 24, 48, and 72. From Week 72 onward, MRI scans will be performed every 48 weeks (i.e., at Week 120, 168, etc.). In addition, mandatory MRI scans will be obtained in patients who withdraw from study treatment (at withdrawal visit) if one was not performed during the prior 4 weeks. Mandatory MRI scans should occur within a window of ± 4 weeks of the scheduled visit, as per the schedules of activities (see [Appendix 1](#), [Appendix 2](#), [Appendix 3](#), and [Appendix 4](#)). At the Week 120 visit for patients switching to PDP OCR treatment, mandatory MRI scans should be obtained within 4 weeks before the Week 120 visit.

The mandatory MRI sequences are comprised of both brain and axial cervical spinal sequences if site technology is available, and data from these scans will contribute measurements for the key MRI secondary endpoints as well as novel exploratory

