endpoints. For details of the mandatory MRI sequences, refer to the MRI Acquisition Procedures Manuals. Axial cervical spine sequences are not required for the first mandatory MRI at screening MRI nor are expected to be included in a historical MRI used for screening (if applicable), but these axial cervical spine sequences should be included in second mandatory MRI scan (considered the baseline MRI).

If site technology is available, in addition to the mandatory MRI sequences, optional, additional sagittal cervical spinal cord MRI sequences may be acquired for baseline, Weeks 24 and 120, at treatment discontinuation, and every 48 weeks in the OLE (according to the yearly schedule as carried over from the double-blind treatment phase). These sagittal cervical spine sequences provide further information on cervical spinal cord lesions and atrophy. Additional optional sagittal cervical spinal cord MRI sequences are not required to accompany the first mandatory MRI at screening MRI nor are expected to be included in a historical MRI used at screening, but these sequences should be included in the second mandatory MRI (considered the baseline MRI) scan. Subjects who choose to participate, an additional signed Informed Consent Form (ICF – denoted as ‘Consent for optional cervical spinal cord MRI scans’ in the master ICF), dedicated to the sagittal cervical spine is required. For details of the additional optional sagittal cervical spine MRI sequences, refer to the MRI Acquisition Procedures Manuals.

During the OLE, MRI mandatory and additional optional sagittal cervical spinal cord scans will be performed every 48 weeks (according to the yearly schedule as carried over from the double-blind treatment phase).

MRI assessments will include, but may not be limited to, T1-weighted scans before and after injection of Gd contrast, fluid-attenuated inversion recovery, proton density-weighted, and T2-weighted scans.

MRI scans will be read by a centralized reading center for efficacy endpoints. The centralized reading center will be blinded to treatment assignment, and the reading will be performed in the absence of clinical information.

Further details on scanning acquisition sequences, methods, handling and transmission of the scans, certification of site MRI radiologist/technicians, and the procedures for the blinded analysis of the scans at the central reading center will be described in a separate MRI Acquisition Procedures Manual.

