4. STATISTICAL ANALYSES

4.1 GENERAL CONSIDERATIONS

As per the EMA guideline on multiplicity issues in clinical trials (EMA, 2017) and the FDA guidance for industry on multiple endpoints in clinical trials (FDA, 2022) multiple primary endpoints are designated as co-primary endpoints if study success is defined by a positive outcome in all primary endpoints.

In this SAP, the terminology co-primary endpoint and co-primary estimand is used although study success is defined by a positive outcome in at least one of the two co-primary endpoints, analogous to multiple primary endpoints.

For all continuous variables for which descriptive statistics are reported, the following will be reported: the number of observations, the mean, median, standard deviation, and minimum and maximum. The 25th and 75th percentiles (Q1 and Q3) will also be reported for selected tables. Descriptive summaries of discrete data will include frequencies expressed in terms of number and percentage of patients.

All primary and secondary efficacy endpoints will be stratified by/adjusted for:

- MRI activity, defined as any T1 Gd+ lesion(s) and/or new and/or enlarging T2 lesion(s) during the screening period (yes vs. no)
- Age (≤ 55 . vs. > 55)
- EDSS score (≤ 6.5 vs. > 6.5)
- Region (two regions: European Union, United Kingdom, and Canada vs. other)

The baseline is defined as the most recent value prior to first dose administration (or up to and including the date of randomization for non-treated patients), unless specified otherwise.

The baseline MRI is defined as the most recent MRI prior to randomization.

For EDSS and 9-HPT, baseline is defined as the most recent value prior to randomization.

There will be no imputation of the baseline outcome value, with the consequence that participants missing the baseline outcome measure will not contribute to the analyses which use change from baseline of a given outcome measure as the dependent variable.

For analysis purposes, the time of treatment discontinuation will be defined as 24 weeks after the last dose prior to the date of treatment discontinuation recorded in the electronic Case Report Form (eCRF).

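### In the MRI-active subgroup the lesion-count models of SAP 4.4.6 carry no baseline lesion information, although a baseline Gd-enhancing count is available; adding it may tighten the rate ratio modestly

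*SAP*

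**What the plan says.** SAP 4.4.6 specifies separate negative binomial models with a log link, one per scheduled visit and one for the total count, for each of the two lesion types. The linear predictor has "as an offset either the log number of MRI scans for Gd-enhancing T1 lesions or log time in years of scan relative to baseline" (the second form being for new or enlarging T2 lesions), together with "an indicator variable for the assigned treatment and the randomization stratification factors as independent variables". No other term is listed. The models are run in all randomized patients and again in the MRI-active subgroup, and SAP 4.4 classes both as exploratory.

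The stratification factors are in SAP 4.1. The one that concerns lesions is "MRI activity, defined as any T1 Gd+ lesion(s) and/or new and/or enlarging T2 lesion(s) during the screening period (yes vs. no"); the others are age (cut at 55), EDSS (cut at 6.5) and region.

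On the data available, SAP 4.1 states: "The baseline MRI is defined as the most recent MRI prior to randomization". Protocol 4.5.10 makes the scan mandatory and includes "T1-weighted scans before and after injection of Gd contrast". The same section lets MRI activity at screening be judged either from "two mandatory MRI scans (performed at least 6 weeks apart, but not more than 24 weeks apart") or from one scan compared with a historical scan up to a year old.

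Other models in the SAP do use a starting value. For the continuous eCOA endpoints (4.4.1): "The fixed effects in the model will include independent variables of randomized treatment, visit, baseline outcome". The T2-volume model (4.3.2) uses the cube root of baseline T2 volume, the brain-volume model (4.3.3) uses the cube root of the Week 24 volume, and the exploratory MRI rate-of-change endpoints (4.4.5) reuse the 4.3.2 estimator.

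**The concern.** Lesion counts usually differ widely between patients, and a patient's count at baseline may say something about later counts. A yes/no flag records only part of that. It does not separate one Gd-enhancing lesion from ten, and it pools patients with enhancing lesions and patients who only had a new or enlarging T2 lesion. In the MRI-active subgroup everyone is a yes, so the flag adjusts for nothing.

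If the baseline count predicts later counts, leaving it out gives a wider confidence interval for the rate ratio than the trial's data allow. Precision is all that is at stake. The model as written is valid, and these endpoints lie outside the testing hierarchy.

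**Working it through.** **1. What baseline lesion information each analysis uses.** The planned model is

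log E(count) = log(offset) + b0 + b1·treatment + c1·MRI activity + c2·age group + c3·EDSS group + c4·region.

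In all randomized patients the c1 term carries a dichotomised baseline lesion measure. In the MRI-active subgroup MRI activity equals 1 for everyone and is absorbed into b0. Age, EDSS and region remain, and none of them is a lesion measure.

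**2. Which baseline covariates exist.**
- Gd-enhancing T1 count: countable on the single baseline scan, because post-contrast T1 imaging is part of it.
- T2 lesion volume: already used as a baseline covariate in SAP 4.3.2.
- New or enlarging T2 count: needs a reference scan, and the screening interval is 6–24 weeks on one route and up to 1 year on the other. There is no count on a common interval.

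**3. The plan's own figures.** The documents give no lesion rate, dispersion, rate ratio or power for these endpoints, so there is nothing to reproduce. The only stated powers are for the primary composite. They reproduce with Schoenfeld's formula (80.1%, 75.6% and 77.9% against 80%, 75.5% and 78%) but have no bearing here.

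**4. Simulation of the gain.** From the documents: N = 1000, 1:1 allocation, and four post-baseline scans in the 144-week phase (Weeks 24, 48, 72 and 120, Protocol 4.5.10). Assumed: mean Gd-enhancing count per scan 0.3 or 0.5; lognormal patient frailty with variance 4 or 8 respectively; correlation ρ between baseline and follow-up frailty 0.3, 0.6 or 0.9; rate ratio 0.30 or 0.05. The simulated MRI-active share was 30–38%, against a planned 350/1000 = 35%. Each setting had 50–60 replicates with a log-scans offset. Age, EDSS and region were left out.

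Model A has treatment and MRI activity. Model B adds log(1 + baseline Gd-enhancing count). The variance change is (SE_B/SE_A)² − 1, where SE is that of the log rate ratio.

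Results at rate ratio 0.30:

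| Mean, frailty variance | ρ | All randomized: SE A → B | Variance change | MRI-active: SE A → B | Variance change |
|---|---|---|---|---|---|
| 0.3, 4 | 0.3 | 0.1257 → 0.1257 | 0.0% | 0.2066 → 0.2064 | −0.1% |
| 0.3, 4 | 0.6 | 0.1248 → 0.1243 | −0.8% | 0.1879 → 0.1856 | −2.4% |
| 0.3, 4 | 0.9 | 0.1208 → 0.1176 | −5.2% | 0.1738 → 0.1648 | −10.1% |
| 0.5, 8 | 0.3 | 0.1258 → 0.1257 | −0.2% | 0.1883 → 0.1873 | −1.0% |
| 0.5, 8 | 0.6 | 0.1223 → 0.1203 | −3.3% | 0.1770 → 0.1712 | −6.5% |
| 0.5, 8 | 0.9 | 0.1179 → 0.1102 | −12.5% | 0.1581 → 0.1392 | −22.5% |

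Percentages come from unrounded SEs. For the last cell, (0.1392/0.1581)² = 0.775, a cut of 22.5%.

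At rate ratio 0.05 the variance change ran from +1.1% to −1.5% in all randomized patients and from +1.0% to −1.9% in the MRI-active subgroup, which is effectively nil.

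**5. Reliability.** A second run of the 0.5, 8, ρ = 0.6 setting gave −8.3% in the MRI-active subgroup against −6.5% above, so single cells carry visible Monte Carlo noise. Mean rate-ratio estimates were 0.29–0.32 for an assumed 0.30 with or without the covariate, as expected for a ratio of means under a log link. A few fits failed. A heavier setting (mean 1.0, variance 8) gave cuts of up to 22.4% and 31.1%, but it implies a 52–55% MRI-active share and is set aside. The new/enlarging T2 endpoint and the T2-volume covariate were not simulated.

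**The case against.** The strongest reply is that this is an efficiency preference about exploratory endpoints. The model is valid, the conclusion is unlikely to change, and the documents cite nothing showing that the baseline count predicts later counts. That stands, and it is why ρ was varied from 0.3 to 0.9 and why no gain at all lies within the range.

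A second reply is that 4.4.6 is not out of line with the SAP. The models that adjust for a starting value mostly analyse change from that value, where such adjustment is natural, whereas the primary Cox model and log-rank test use the randomization factors alone. This weakens the argument from consistency. It does not touch the main fact, which is that the only lesion-related factor is constant in the MRI-active subgroup.

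A reader might also infer stronger things that the documents do not support:
- *That the models ignore baseline lesion activity altogether.* In all randomized patients the MRI-activity factor is in the model.
- *That the trial already holds a baseline count for both lesion types.* It does for Gd-enhancing lesions. For new or enlarging T2 lesions the reference interval differs by screening route.
- *That the covariate costs nothing.* SAP 4.1 does not impute baseline outcome values, so patients without one would leave the fit, and by-visit counts may be too sparse for a stable fit.
- *That the gain is reliably large.* If each patient's lesion rate is taken as fixed from baseline onward, with three scans and rate ratio 0.3, variance cuts of 8–30% (all randomized) and 14–36% (MRI-active) can be produced. Those settings favour the covariate and do not fit together. They take a mean baseline count of 1.2 in 350 MRI-active patients and 0.6 overall, but MRI-inactive patients have no Gd-enhancing lesion at screening by definition, so the overall mean would be 0.35 × 1.2 = 0.42.

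**Conclusion.** The point holds as a modest precision suggestion. SAP 4.4.6 uses no baseline lesion information in the MRI-active subgroup and only a yes/no flag in all randomized patients, while a baseline Gd-enhancing count is obtainable from a mandatory scan. Under the assumptions above, the variance of the log rate ratio changes by about +1% to −12.5% in all randomized patients and about +1% to −22.5% in the MRI-active subgroup. The upper ends need strong persistence from baseline to follow-up, and the gain is near zero if treatment almost abolishes lesions. For the T2 models the case rests on reasoning, not on a calculation. Bias, type I error and the meaning of the rate ratio are not at issue.

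**What to change.** In SAP 4.4.6, add log(1 + baseline Gd-enhancing T1 lesion count) as a covariate to the Gd-enhancing and the new/enlarging T2 models, chiefly for the MRI-active subgroup and the overall counts. In the T2 model the cube root of baseline T2 volume, the scale of SAP 4.3.2, may be added as an option. Do not use a screening count of new or enlarging T2 lesions. Leave the offsets as they are, and state that a by-visit fit that does not converge reverts to the current model.

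The cost is one or two terms in the model statement. Patients without a baseline MRI value drop out of the fit, which should be rare because the scan is mandatory and is taken early enough to be repeated (Protocol 4.5.10). The change should be made before database lock and unblinding, since a covariate added later would look data-driven. If the sponsor prefers the present model, one sentence of justification in 4.4.6 would be enough.
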